4.3 TREATMENT COMPLIANCE

Compliance will be assured by administration of all trial medication at the trial center by the investigator or an authorised designee. The measured plasma concentrations will provide additional confirmation of compliance.

Subjects who are non-compliant (for instance, who do not appear for scheduled visits or violate trial restrictions) may be removed from the trial and the eCRF will be completed accordingly (for further procedures, please see [Section 3.3.4.1](#)).

Boehringer Ingelheim
BI Trial No.: 1297.13
c11534380-01

23 Aug 2016

Trial Protocol

Page 29 of 58

Proprietary confidential information © 2016 Boehringer Ingelheim International GmbH or one or more of its affiliated companies

5. VARIABLES AND THEIR ASSESSMENT

5.1 TRIAL ENDPOINTS

5.1.1 Primary Endpoint(s)

The following primary endpoints for PK will be determined for BI 695501 administered via PFS and AI:

- AUC_{0-1368} (area under the concentration-time curve of the analyte in plasma over the time interval from 0 to 1368 hours after dose)
- C_{max} (maximum measured concentration of the analyte in plasma)
- $AUC_{0-\infty}$ (area under the concentration-time curve of the analyte in plasma over the time interval from 0 extrapolated to infinity)

5.1.2 Secondary Endpoints

For safety:

Number (proportion) of subjects with drug-related TEAEs occurring from Day 1 through Day 70.

For PK/immunogenicity:

No secondary endpoints for PK and immunogenicity are defined.

Boehringer Ingelheim
BI Trial No.: 1297.13
c11534380-01

23 Aug 2016

Trial Protocol

Page 30 of 58

Proprietary confidential information © 2016 Boehringer Ingelheim International GmbH or one or more of its affiliated companies

5.2 ASSESSMENT OF EFFICACY

No efficacy will be evaluated.

5.3 ASSESSMENT OF SAFETY

5.3.1 Physical examination

A physical examination will be performed at the visits indicated in the [Flow Chart](#). At the screening visit, the medical examination will include documentation of subject information, informed consent, demographics including height and body weight, smoking and alcohol history, relevant medical history and concomitant therapy, review of inclusion and exclusion criteria, review of vital signs (BP, PR, temperature), 12-lead ECG, laboratory tests (including drug and virus screening, IGRA-T), and a physical examination. At the e.o.t. examination, the medical examination will include review of vital signs, 12-lead ECG, laboratory tests (including IGRA-T), and a physical examination with determination of weight. Adverse events and concomitant therapies will be assessed throughout the trial. The physical examination will include assessment of general appearance, skin, head, neck, throat, lymph nodes, cardiovascular and neurological systems, thyroid gland, musculoskeletal system/limbs, respiratory tract and abdomen.

5.3.2 Vital Signs

Systolic and diastolic BP as well as PR or heart rate (heart rate is considered to be equal to PR) will be measured by means of a validated BP device at the times indicated in the

Boehringer Ingelheim
BI Trial No.: 1297.13
c11534380-01

23 Aug 2016

Trial Protocol

Page 31 of 58

Proprietary confidential information © 2016 Boehringer Ingelheim International GmbH or one or more of its affiliated companies

[Flow Chart](#), after subjects have rested for at least 5 min in a supine position. All recordings should be made using the same type of BP recording instrument on the same arm if possible.

The method of measuring body temperature (oral/aural) should be consistent at a specific trial site.

5.3.3 Safety laboratory parameters

For the assessment of laboratory parameters, blood and urine samples will be collected by the trial site at the time points indicated in the Flow Chart after the subjects have fasted for at least 10 hours (or 4 hours before admission on Day -1). Overnight fasting is not required at the discretion of the investigator or designate for retests.

Required sample volumes for safety/serology laboratory assessments may vary between local laboratories. Sample amount may be exceeded if unscheduled (additional) monitoring of laboratory results is warranted.

The parameters that will be determined are listed in [Table 5.3.3: 1](#) and [Table 5.2.3: 2](#). Reference ranges will be provided in the ISF, Section 10.

Manual differential white blood cell count or urine sediment examinations will only be performed if there is a relevant abnormality in the automatic blood cell count or in the urinalysis, respectively.

Boehringer Ingelheim
BI Trial No.: 1297.13
c11534380-01

23 Aug 2016

Trial Protocol

Page 32 of 58

Proprietary confidential information © 2016 Boehringer Ingelheim International GmbH or one or more of its affiliated companies

Table 5.3.3: 1 Routine laboratory tests

Functional lab group	Test name
Hematology	Hematocrit Hemoglobin Red blood cell count (RBC) White blood cell count (WBC) Platelet count
Automatic WBC differential (relative)	Neutrophils, eosinophils, basophils, monocytes, lymphocytes
Manual differential WBC (at the investigator's discretion)	Neutrophils, eosinophils, basophils, monocytes, lymphocytes
Coagulation ¹	Activated partial thromboplastin time (Aptt) Prothrombin time (Quick's test and international normalized ratio [INR]) Fibrinogen
Enzymes	Aspartate aminotransferase (AST/GOT) Alanine aminotransferase (ALT/GPT) Gamma glutamyl transferase (GGT) Creatine kinase (CK) CK-MB, only if CK is elevated
Substrates	Plasma glucose Creatinine Total bilirubin Direct bilirubin Bilirubin indirect Total protein Albumin C-Reactive Protein (CRP) Total cholesterol
Electrolytes	Sodium Potassium Calcium
Serum Pregnancy test (only for female subjects of childbearing potential) at screening and if urine pregnancy test is positive	Human Serum Chorionic Gonadotropin
Urinalysis (Stix)	Urine nitrite Urine protein Urine glucose Urine erythrocytes
Urine Pregnancy test (only for female subjects of childbearing potential) at randomization and continued as indicated in the Flow Chart (including EoT	Human Chorionic Gonadotropin in the urine

¹ at screening only

The tests listed in [Table 5.3.3: 1](#) will be performed at screening, and as part of the end of trial examination.

Boehringer Ingelheim
BI Trial No.: 1297.13
c11534380-01

23 Aug 2016

Trial Protocol

Page 33 of 58

Proprietary confidential information © 2016 Boehringer Ingelheim International GmbH or one or more of its affiliated companies

The tests listed in [Table 5.3.3: 2](#) are exclusionary laboratory tests which may be repeated as required. The results will not be entered in the eCRF/database and will not be reported in the CTR. Except for drug screening, it is planned to perform these tests during screening only. Drug screening will be performed at screening and prior to treatment period on Day -1.

Table 5.2.3: 2 Exclusionary laboratory tests

Functional lab group	Test name
Drug screening (urine)	Amphetamine
	Barbiturates
	Benzodiazepine
	THC
	Cocaine
	Methadone
	Methamphetamines
	Opiates
	PCP
	Tricyclic antidepressants
Infectious serology (blood)	Hepatitis B surface antigen (qualitative)
	Hepatitis B core antibody (qualitative)
	Hepatitis C antibodies (qualitative)
	HIV-1 and HIV-2 antibody (qualitative)
Tuberculosis	IGRA-T (e.g. QuantiFERON®-TB Gold IT Test)

The following laboratory parameters will be analyzed at all other visits indicated in [Flow Chart](#):

- Serum chemistry: creatinine, alkaline phosphatase, AST, ALT, GGT, CK, bilirubin (total and direct), glucose, total cholesterol, total protein, albumin, sodium, potassium, calcium
- Hematology: hemoglobin, hematocrit, platelets, red blood cells, white blood cells, lymphocytes, neutrophils
- Urinalysis: protein, glucose, erythrocytes

To encourage compliance with alcoholic restrictions, a breath alcohol test will be performed prior to the treatment period, and may be repeated at any time during the trial at the discretion of the investigator or designee. Alternately, alcohol screening may be done as part of urine drug screening. The results will not be included in the CTR.

The laboratory tests listed in [Table 5.3.3: 1](#) and Table 5.3.3: 2 will be performed at the local site laboratory with the exception of the drug screening tests. These tests will be performed at the trial sites.

Laboratory data will be transmitted electronically from the laboratory to the trial site.

5.3.4 Electrocardiogram

Twelve-lead ECGs (I, II, III, Avr, Avl, Avf, V1 – V6) will be recorded using a computerized electrocardiograph as scheduled in the Flow Chart.

Boehringer Ingelheim
BI Trial No.: 1297.13
c11534380-01

Trial Protocol

23 Aug 2016
Page 34 of 58

Proprietary confidential information © 2016 Boehringer Ingelheim International GmbH or one or more of its affiliated companies

ECGs will be recorded after the subjects have rested for at least 5 minutes in a supine position and will always precede blood sampling.

All locally printed ECGs will be evaluated by the investigator or a designee. ECGs may be repeated for quality reasons (like alternating current artefacts, muscle movements, electrode dislocation) and the only valid ECG will be used for analysis and reported in CRF. Additional (unscheduled) ECGs may be collected by the investigator for safety reasons.

Abnormal findings will be reported as AEs (during the trial) or baseline conditions (at screening) if judged clinically relevant by the investigator. Any ECG abnormalities, judged as clinically relevant, will be monitored carefully and, if necessary, the subject will be removed from the trial and will receive the appropriate medical treatment. A physician familiar with interpretation of ECG will evaluate the ECG from a clinical perspective and the result (whether the ECG result is normal, abnormal not clinically relevant or abnormal clinically relevant) will be recorded in the appropriate section of the eCRF. The digitally recorded ECGs will be electronically stored.

5.3.5 Other safety parameters

Local tolerability

Injection site reaction assessment will be performed by investigator or site staff according to “swelling”, “induration”, “heat”, “redness”, “pain”, or “other findings”. Tolerability will be assessed at Day 1 from the time of the injection until Day 2. If any injection site reactions are observed, these findings should also be reported on the AE eCRF page.

5.3.6 Immunogenicity evaluation

The following further parameters of interest will be evaluated:

- The proportion of subjects with antidrug antibodies (ADAs) at baseline (pre-dose), Day 22, and Day 57.
- ADA titers of ADA positive subjects at baseline (pre-dose), Day 22, and Day 57
- The proportion of subjects with neutralizing antidrug antibodies (nAbs) at baseline (pre-dose), Day 22, and Day 57

5.3.7 Assessment of adverse events

5.3.7.1 Definitions of AEs

Adverse event

An adverse event (AE) is defined as any untoward medical occurrence in a subject or clinical investigation subject administered a medicinal product and which does not necessarily have to have a causal relationship with this treatment.

An AE can therefore be any unfavourable and unintended sign (including an abnormal laboratory finding), symptom, or disease temporally associated with the use of a medicinal product, whether or not considered related to the medicinal product.

Boehringer Ingelheim
BI Trial No.: 1297.13
c11534380-01

23 Aug 2016

Trial Protocol

Page 35 of 58

Proprietary confidential information © 2016 Boehringer Ingelheim International GmbH or one or more of its affiliated companies

Adverse reaction

An adverse reaction is defined as a response to a medicinal product which is noxious and unintended. Response in this context means that a causal relationship between a medicinal product and an adverse event is at least a reasonable possibility. Adverse reactions may arise from use of the product within or outside the terms of the marketing authorisation or from occupational exposure. Conditions of use outside the marketing authorization include off-label use, overdose, misuse, abuse and medication errors.

Serious adverse event

A serious adverse event (SAE) is defined as any AE which:

- results in death,
 - is life-threatening, this refers to an event in which the subject was at risk of death at the time of the event; it does not refer to an event that hypothetically might have caused death if more severe.
 - requires inpatient hospitalisation or
 - prolongation of existing hospitalisation,
 - results in persistent or significant disability or incapacity, or
 - is a congenital anomaly / birth defect,
- or
- is to be deemed serious for any other reason if it is an important medical event when based upon appropriate medical judgment which may jeopardise the subject and may require medical or surgical intervention to prevent one of the other outcomes listed in the above definitions.

Medical and scientific judgement should be exercised in deciding whether other situations should be considered serious reactions, such as important medical events that might not be immediately life threatening or result in death or hospitalisation but might jeopardise the patient or might require intervention to prevent one of the other outcomes listed above. Examples of such events are intensive treatment in an emergency room or at home for allergic bronchospasm, blood dyscrasias or convulsions that do not result in hospitalisation or development of dependency or abuse. Any suspected transmission via a medicinal product of an infectious agent is also considered a serious adverse reaction.

AEs considered “Always Serious”

Cancers of new histology and exacerbations of existing cancer must be reported as a serious event regardless of the duration between discontinuation of the drug and the occurrence of the cancer.

In accordance with the European Medicines Agency initiative on Important Medical Events, Boehringer Ingelheim has set up a list of further AEs, which by their nature, can always be considered to be “serious” even though they may not have met the criteria of an SAE as given above.

The latest list of “Always Serious AEs” can be found in the ISF. A copy of the latest list of “Always Serious AEs” will be provided to you upon request.

Boehringer Ingelheim
BI Trial No.: 1297.13
c11534380-01

23 Aug 2016

Trial Protocol

Page 36 of 58

Proprietary confidential information © 2016 Boehringer Ingelheim International GmbH or one or more of its affiliated companies

Adverse events of special interest (AESIs)

The term AESI relates to any specific AE that has been identified at the project level as being of particular concern for prospective safety monitoring and safety assessment within this trial, e.g. the potential for AEs based on knowledge from other compounds in the same class. AESI need to be reported to the sponsor's Pharmacovigilance Department within the same timeframe that applies to SAE, please see above.

The following are considered as AESIs:

1. Hepatic injury

A hepatic injury is defined by the following alterations of hepatic laboratory parameters:

- an elevation of AST and/or ALT ≥ 3 fold ULN combined with an elevation of total bilirubin ≥ 2 fold ULN measured in the same blood draw sample, and/or
- marked peak aminotransferase (ALT, and/or AST) elevations ≥ 10 fold ULN

These lab findings constitute a hepatic injury alert and the subjects showing these lab abnormalities need to be followed up according to the "DILI checklist" provided in the ISF. In case of clinical symptoms of hepatic injury (icterus, unexplained encephalopathy, unexplained coagulopathy, right upper quadrant abdominal pain, etc.) without lab results (ALT, AST, total bilirubin) available, the Investigator should make sure these parameters are analysed, if necessary in an unscheduled blood test. Should the results meet the criteria of hepatic injury alert, the procedures described in the DILI checklist should be followed.

2. Anaphylactic reactions

3. Serious infection (defined as infections requiring IV antibiotics or meeting the regulatory definition of a SAE)

4. Hypersensitivity reactions

Intensity of AEs

The intensity of the AE should be judged based on the following:

Mild:	Awareness of sign(s) or symptom(s) that is/are easily tolerated
Moderate:	Enough discomfort to cause interference with usual activity
Severe:	Incapacitating or causing inability to work or to perform usual activities

Causal relationship of AEs

The definition of an adverse reaction implies at least a reasonable possibility of a causal relationship between a suspected medicinal product and an adverse event. An adverse reaction, in contrast to an adverse event, is characterised by the fact that a causal relationship between a medicinal product and an occurrence is suspected.

Medical judgment should be used to determine the relationship, considering all relevant factors, including pattern of reaction, temporal relationship, de-challenge or re-challenge, confounding factors such as concomitant medication, concomitant diseases and relevant history.

Arguments that may suggest that there is a reasonable possibility of a causal relationship could be:

- The event is consistent with the known pharmacology of the drug

Boehringer Ingelheim
BI Trial No.: 1297.13
c11534380-01

23 Aug 2016

Trial Protocol

Page 37 of 58

Proprietary confidential information © 2016 Boehringer Ingelheim International GmbH or one or more of its affiliated companies

- The event is known to be caused by or attributed to the drug class.
- A plausible time to onset of the event relative to the time of drug exposure.
- Evidence that the event is reproducible when the drug is re-introduced
- No medically sound alternative aetiologies that could explain the event (e.g. pre-existing or concomitant diseases, or co-medications).
- The event is typically drug-related and infrequent in the general population not exposed to drugs (e.g. Stevens-Johnson syndrome).
- An indication of dose-response (i.e. greater effect size if the dose is increased, smaller effect size if dose is diminished).

Arguments that may suggest that there is no reasonable possibility of a causal relationship could be:

- No plausible time to onset of the event relative to the time of drug exposure is evident (e.g. pre-treatment cases, diagnosis of cancer or chronic disease within days / weeks of drug administration; an allergic reaction weeks after discontinuation of the drug concerned)
- Continuation of the event despite the withdrawal of the medication, taking into account the pharmacological properties of the compound (e.g. after 5 half-lives). Of note, this criterion may not be applicable to events whose time course is prolonged despite removing the original trigger.
- Additional arguments amongst those stated before, like alternative explanation (e.g. situations where other drugs or underlying diseases appear to provide a more likely explanation for the observed event than the drug concerned).
- Disappearance of the event even though the study drug treatment continues or remains unchanged.

5.3.7.2 Adverse event collection and reporting

AE Collection

The Investigator shall maintain and keep detailed records of all AEs in their subject files. The following must be collected and documented on the appropriate CRF(s) by the Investigator:

- From signing the informed consent onwards through the Residual Effect Period (REP), until individual subject's end of trial:
-all AEs (serious and non-serious) and all AESIs.
However, if an individual subject discontinues trial assessments but stays in the trial (i.e. if further visits incl. telephone visits, or vital status assessments are planned) from then on and until the individual subject's end of the trial the Investigator must report related SAEs and related AESIs.
- After the individual subject's end of trial:
the Investigator does not need to actively monitor the patient for AEs but should only report relevant SAEs and relevant AESIs of which the Investigator may become aware of.

[figure not shown]
Boehringer Ingelheim
BI Trial No.: 1297.13
c11534380-01

Trial Protocol

23 Aug 2016

Page 38 of 58

Proprietary confidential information © 2016 Boehringer Ingelheim International GmbH or one or more of its affiliated companies

- The REP is defined as 10 weeks after the last trial medication application. All AEs which occurred through the treatment phase and throughout the REP will be considered as on treatment, please see [section 7.3.4](#). Events which occurred after the REP will be considered as post treatment events.

AE reporting to sponsor and timelines

The Investigator must report SAEs, AESIs, and non-serious AEs which are relevant for the reported SAE or AESI, on the BI SAE form via fax immediately (within 24 hours) to the sponsor's/sponsor designee's unique entry point (contact details will be provided in the ISF). The same timeline applies if follow-up information becomes available. In specific occasions the Investigator could inform the sponsor upfront via telephone. This does not replace the requirement to complete and fax the BI SAE form.

With receipt of any further information to these events, a follow-up SAE form has to be provided. For follow-up information the same rules and timeline apply as for initial information.

Information required

For each AE, the Investigator should provide the information requested on the appropriate CRF pages and the BI SAE form. The Investigator should determine the causal relationship of AE to the trial medication.

The following should also be recorded as an (S)AE in the CRF and SAE form (if applicable):

- Worsening of the underlying disease or of other pre-existing conditions
- Changes in vital signs, ECG, physical examination and laboratory test results, if they are judged clinically relevant by the Investigator.

If such abnormalities already pre-exist prior trial inclusion they will be considered as baseline conditions.

All (S)AEs, including those persisting after individual subject's end of trial must be followed up until they have resolved, have been sufficiently characterised, or no further information can be obtained.

Pregnancy

In rare cases pregnancy may occur in a clinical trial. Once a subject has been enrolled into this clinical trial and has taken trial medication, the Investigator must report immediately

Boehringer Ingelheim
BI Trial No.: 1297.13
c11534380-01

23 Aug 2016

Trial Protocol

Page 39 of 58

Proprietary confidential information © 2016 Boehringer Ingelheim International GmbH or one or more of its affiliated companies

(within 24 hours) a potential drug exposure during pregnancy (DEDP) to the sponsor's/sponsor designee's unique entry point (contact details will be provided in the ISF). The Pregnancy Monitoring Form for Clinical Trials (Part A) should be used.

The outcome of the pregnancy associated with the drug exposure during pregnancy must be followed up and reported to the sponsor's unique entry point on the Pregnancy Monitoring Form for Clinical Trials (Part B).

The ISF will contain the Pregnancy Monitoring Form for Clinical Trials (Part A and B).

As pregnancy itself is not to be reported as an AE, in the absence of an accompanying SAE and/or AESI, only the Pregnancy Monitoring Form for Clinical Trials and not the SAE form is to be completed. If there is an SAE and/or AESI associated with the pregnancy an SAE form must be completed in addition.

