3. DESCRIPTION OF DESIGN AND TRIAL POPULATION

3.1 OVERALL TRIAL DESIGN AND PLAN

The trial will be performed as a randomized, single-dose, open-label, parallel arm trial in healthy male and female subjects aged ≥ 18 to ≤ 65 years, in order to evaluate and to compare the PK and safety of the test treatment (A/BI 695501 in autoinjector) to the reference treatment (B/ BI 695501 in prefilled syringe) in a broad weight range . The subjects will be allocated to 3 weight groups: ≤ 60.0 kg, $>60.0 - <90.0$ kg, ≥ 90.0 kg. The subjects will be randomly allocated to one of the two treatments (A or B). The treatments will be one 40 mg BI 695501/ autoinjector (A) or one 40 mg BI 695501 / prefilled syringe (B) followed by approximately 57 days of observation period.

It is planned to include 160 healthy male and female subjects (at least 30% of each gender will be included in the study) with a broad range of weight for the primary analysis report describing the PK profiles of BI 695501 given in a prefilled syringe and an autoinjector as well as the assessments of safety and immunogenicity. All efforts will be made to enroll subjects in all subgroups, in order to ensure a wide distribution of weight in the study.

This trial will have a screening period of up to 28 days. The subject will check-in to the trial center on Day -1, will be dosed on Day 1 and be resident until the Day 8 discharge procedures are complete. All subjects will remain in the clinic until day 8 after dosing. The subject will then return to the clinic for 7 ambulatory visits on Days 10, 15, 22, 29, 36, 43 and 57 (e.o.t.).

Additionally, all AEs, regardless of relatedness, will be collected until 10 weeks after the administration of trial medication. Adverse events not fully resolved at the Safety Follow-up visit will be followed until recovery or in case of persistency, sufficient characterization has been achieved and the investigator and medical monitor agree to not pursue them further.

For details for treatments to be administered refer to [Section 4.1](#).

An overview of all relevant trial activities is provided in [Flow Chart](#). For visit schedule and details of trial procedures at selected visits, refer to [Section 6.1](#) and [Section 6.2](#), respectively.

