6.2.3 Follow Up Period and Trial Completion

For AE assessment, laboratory tests, recording of ECG and vital signs, and physical examination during the end of treatment (e.o.t.) visit (day 57), see [Sections 5.3.1 to 5.3.5](#).

Subjects who discontinue trial participation before the end of the planned observational period but not withdraw consent - should undergo the e.o.t. visit and Safety Follow-up (end of trial) visit 10 weeks after administration of the trial medication.

All abnormal values (including laboratory parameters) that are judged clinically relevant by the investigator will be monitored using the appropriate tests until a return to a medically acceptable level is achieved. Adverse events persisting after trial completion must be monitored until they have normalized or have been sufficiently characterized.

The end of the trial as a whole is defined by the ‘last regular visit completed by last subject’ or ‘end date of the last open AE’ or ‘date of the last follow-up test’ or ‘date of an AE has been decided as sufficiently followed-up’, whichever is latest.

Long-term safety follow-up observational period will continue for 10 weeks after BI 695501 administration to collect AEs (SAEs).

The subjects are to be instructed to contact the investigator or his/her designee in case of occurrence of any AEs, any additional concomitant drug or if they undergo any medical treatment or any surgical procedure during the observational period until the safety follow-up visit call. Subjects will be contacted by the investigator or designee 10 weeks after administration of the trial medication to collect the information on subject’s wellbeing and document all AEs (SAEs) and concomitant medication.

All AEs, serious and non-serious, will be followed up until they have normalized or been sufficiently characterized and documented in the safety database.

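### Protocol 5.3.7.2 narrows AE collection for subjects who stop assessments but stay in the trial, against the all-AE rule elsewhere, so the Day 70 secondary endpoint may be slightly undercounted

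*Protocol*

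**What the plan says.** The secondary endpoint in Protocol 5.1.2 is: "Number (proportion) of subjects with drug-related TEAEs occurring from Day 1 through Day 70". It has no seriousness condition. Protocol 7.3.4 puts every treated subject in the Safety Analysis Set, and SAP 15 repeats the endpoint on that set.

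Protocol 5.3.7.2, under its AE collection heading, first asks for "all AEs (serious and non-serious) and all AESIs" from consent through the residual effect period (REP) to the subject's end of trial. "The REP is defined as 10 weeks after the last trial medication application", which is the Day 70 horizon. An exception follows: "if an individual subject discontinues trial assessments but stays in the trial", meaning that a visit, telephone visit or vital-status check is still planned, then from that time "the Investigator must report related SAEs and related AESIs". A separate bullet covers the period after the individual end of trial.

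Other sections carry no such exception. Protocol 3.1 says that "all AEs, regardless of relatedness, will be collected until 10 weeks after the administration of trial medication"; Protocol 2.3 and SAP 3.1 say the same. Protocol 6.2.3 gives subjects who stop early without withdrawing consent the end-of-treatment visit and the Week 10 follow-up. It describes the Week 10 contact as one to "document all AEs (SAEs) and concomitant medication".

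**The concern.** The collection rule for one group of subjects is narrower than the endpoint it has to feed. Under the exception, a related, non-serious event that is not an AESI and starts after the subject stops assessments need not be entered in the CRF. The endpoint would count it.

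The subject remains in the denominator. No analysis rule repairs the gap: Protocol 7.5.1 imputes a missing relationship as related, and SAP 15.1.1.1 sets missing intensity to severe, but neither can restore an event that was never recorded. The TEAE window in SAP 15.1 makes no allowance for early stopping. The proportion could therefore be biased downward, and the comparison between devices could shift if stopping differed by arm. Two sites could also apply different rules, each complying with some part of the protocol.

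**Working it through.** **Step 1. Do early stoppers fall under the exception?** It needs a subject who stops assessments while some contact is still planned. Protocol 6.2.3 plans the Week 10 contact for early stoppers who do not withdraw consent, so they can be in this status. Subjects who withdraw consent have no further assessments (Protocol 3.3.4.1) and are outside it.

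**Step 2. Which events would be lost?**
- Related SAEs and related AESIs are still required. AESIs include hypersensitivity reactions with no seriousness condition (Protocol 5.3.7.1).
- The endpoint counts subjects once, so anyone with a related TEAE before stopping is already counted.
- What remains is a subject whose first related TEAE comes after stopping, is neither serious nor an AESI, and is not followed by a related SAE or AESI.

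**Step 3. How large could it be?** The documents give no expected rate for this endpoint and no dropout rate for this trial, so there is no figure of the plan to reproduce. For illustration, if only the exception is followed:

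missed subjects per arm = 80 × d × p × f; loss in percentage points = 100 × d × p × f

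- 80: planned maximum per arm (Protocol 3.2).
- d: share who stop assessments but stay in the trial. Assumed 2-10%. The middle value is 5/71 = 7.0%, from 71 treated and 66 completed in trial 1297.6 (Protocol 1.2). Those results were preliminary, so this is not a stated dropout rate.
- p: true share with a related TEAE. Assumed 10-50%, equal in stoppers and others.
- f: share of those who fit the last item of step 2. Assumed 10-50%.

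| Case | d | p | f | Missed per arm | Loss (points) |
|---|---|---|---|---|---|
| Low | 2% | 10% | 10% | 80 × 0.02 × 0.10 × 0.10 = 0.02 | 0.02 |
| Middle | 7.0% | 30% | 25% | 80 × 0.0704 × 0.30 × 0.25 = 0.42 | 0.53 |
| High | 10% | 50% | 50% | 80 × 0.10 × 0.50 × 0.50 = 2.0 | 2.5 |

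As a fraction of the true proportion the loss is d × f, at most 0.10 × 0.50 = 5%.

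**Step 4. Arm difference.** With equal d, p and f in both arms the bias is zero. With 10% stopping in one arm, none in the other and f = 50%, it is 100 × 0.10 × p × 0.50 = 0.5 points at p = 10% and 2.5 points at p = 50%. The standard error of the difference, 100 × √(2p(1−p)/80), is 4.7 points at p = 10% and 7.9 at p = 50%.

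**Step 5. If sites follow Protocol 2.3, 3.1 and 6.2.3 and SAP 3.1,** all AEs are collected to Week 10 and the loss from this rule is zero.

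**The case against.** The strongest reply is that the protocol already requires what the endpoint needs. Three of its sections and the SAP ask for all AEs to Week 10, Protocol 6.2.2 has AEs assessed continuously to the end of trial, and 6.2.3 is the text specific to the Week 10 contact. The exception states what must be reported and does not forbid recording more, and 5.3.7.2 opens by requiring detailed records of all AEs in the subject files. This stands against any claim that events will be lost. It does not remove the conflict: the exception sits in the detailed collection section, qualifies the all-AE rule just before it, and is addressed to these very subjects. If it is only a minimum, recording the other events is left to discretion at open-label sites.

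The second reply is that little is at stake. There is one injection, subjects stay in the unit to Day 8, injection-site reactions are assessed through Day 2, both arms receive the same drug and dose, and safety is analysed descriptively. All of this stands and is why the likely effect is small.

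A reader might also infer that the endpoint is undercounted for early stoppers in general, by as much as the 7% who may stop. The documents do not support that. Consent withdrawals fall outside the exception. The reasons why 5 of 71 were not among the completers are not given. A 7-point loss would need every stopper to have a first related, non-serious, non-AESI event after stopping.

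**Conclusion.** The point holds as an internal contradiction with a possible undercount, not a certain one. Read alone, the 5.3.7.2 exception is narrower than the secondary endpoint; read with the other sections, its effect depends on which text a site follows, and no precedence is stated.

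If the exception is followed, the loss is about 0.02 to 2.5 percentage points per arm, with about 0.5 in the middle case. These figures rest on assumed values of d, p and f, none of which the documents supply. Bias in the arm difference requires unequal stopping, event rates or timing between arms, which nothing in the documents predicts, and in the extreme case shown it stays below one standard error. The inconsistency should be corrected because collection ought to match the endpoint, not because the result is likely to change.

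**What to change.** Reconcile the sections by removing the exception in Protocol 5.3.7.2 for the period up to Day 70. State there that all AEs, serious and non-serious, are collected until 10 weeks after dosing for every dosed subject who has not withdrawn consent, including those who have stopped assessments, using the Week 10 contact already planned in 6.2.3.

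Leave the bullet on the period after the individual end of trial as it is. It already has its own rule, and moving the related-events wording there would create a new conflict.

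The cost is one sentence in the protocol, with notice to the two sites. No visit is added, and SAP 3.1 already states the full rule.
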